4.1 General Considerations

Treatment groups (and their labels to be displayed in Tables, Figures, Listings) are defined as follows:

- for all primary and secondary efficacy analyses and analyses of QoL variables unless otherwise indicated:

Randomized Planned Treatment Group	Treatment Label					
	Induction Period	Maintenance /Escalation Period	Response Assessment/ Dose Hold Period		Final Assessment Period	
			0	12		24
	(in weeks)					
(1) - Placebo at Week 0, 1, 2, 3, 4, 6, 8 (and / M1095 120 mg at Week 12, 14, 16 and Q4W)	Plac/120mg (x4), Q4					
(6) - Secukinumab 300 mg at Week 0, 1, 2, 3, 4, 8 (and 12 and Q4W)	Secukinumab					
(2) - M1095 30 mg at Week 0, 2, 4, 8 (and (2a) Q4W if no escalation at Week 12) (2b) M1095 120 mg Q4W if escalation at Week 12)	30mg (x4), Q4					
(3) - M1095 60 mg at Week 0, 2, 4, 8 (and (3a) Q4W if no escalation at Week 12) (3b) M1095 120 mg Q4W if escalation at Week 12)	60mg (x4), Q4					
(4) - M1095 120 mg at Week 0, 2, 4, 8 (and 12 and Q8W)	120mg (x4), Q8					
(5) - M1095 120 mg Q2W at Week 0, 2, 4, 6, 8, 10 (and 12 and Q4W)	120mg (x6), Q4					

Table 4.1: Randomized Planned Treatment Groups and their Labels for each Treatment Period for Primary, Secondary Efficacy Analyses and Exploratory Analyses of QoL Variables.

- for all safety analyses unless otherwise indicated:

Table 4.2: Actual Treatment Groups for the Induction Period and their Labels for Safety Analyses of the Induction Period

Actual Treatment Group ^a	Treatment Label
	Induction Period (Week 0-12)
(1) - Placebo at Week 0, 1, 2, 3, 4, 6, 8	Placebo
(6) - Secukinumab 300 mg at Week 0, 1, 2, 3, 4, 8	Secukinumab
(2) - M1095 30 mg at Week 0, 2, 4, 8	30mg (x4), Q4
(3) - M1095 60 mg at Week 0, 2, 4, 8	60mg (x4), Q4
(4) - M1095 120 mg at Week 0, 2, 4, 8	120mg (x4), Q8
(5) - M1095 120 mg Q2W at Week 0, 2, 4, 6, 8, 10	120mg (x6), Q4
	Total M1095 ^b

a: Subjects will be assigned to a treatment group based on the actual treatment they received most during the induction period.

b: Total M1095 will include the subjects who receive M1095 treatment during the induction period i.e. (2), (3), (4) and (5).

Table 4.3: Actual Treatment Groups for the Overall Period and their Labels for Safety Analyses of the Overall Period

Actual Treatment Group ^a	Treatment Label
	Overall Period (Week 0-52)
(1) - Placebo at Week 0, 1, 2, 3, 4, 6, 8 (and M1095 120 mg at Week 12, 14, 16 and Q4W)	Plac/120mg (x4), Q4 ^b
(6) - Secukinumab 300 mg at Week 0, 1, 2, 3, 4, 8 (and 12 and Q4W)	Secukinumab
(2) - M1095 30 mg at Week 0, 2, 4, 8 (2a) and Q4W if no escalation at Week 12 (2b) and M1095 120 mg Q4W if escalation at Week 12	30mg (x4), Q4
(3) - M1095 60 mg at Week 0, 2, 4, 8 (3a) and Q4W if no escalation at Week 12 (3b) and M1095 120 mg Q4W if escalation at Week 12	60mg (x4), Q4
(4) - M1095 120 mg at Week 0, 2, 4, 8 (and 12 and Q8W)	120mg (x4), Q8
(5) - M1095 120 mg Q2W at Week 0, 2, 4, 6, 8, 10 (and 12 and Q4W)	120mg (x6), Q4
	Total M1095 ^c

a: Subjects will be assigned to a treatment group based on the actual treatment they received most during the overall period for all treatment groups except for (1), (2b) and (3b). Regarding (2b) and (3b), subjects will be assigned to a treatment group based on the actual treatment they received most during the induction period.

b: Plac/120 mg (x4), Q4 include all subjects who were mostly administered M1095 120 mg from Week 12 to Week 44 having received placebo during the induction period. The data will only be presented from Week 12 onwards for this treatment group.

c: Total M1095 will include all subjects who received M1095 at any time during the study i.e. (1), (2), (3), (4) and (5).

All pairwise treatment comparisons will be two-sided at the 5% level, without adjustment for multiplicity unless otherwise specified.

All primary/secondary efficacy and exploratory QoL endpoints will be presented in tables including visits from Week 0 to Week 52 as follows: 0, **1, 2, 3, 4, 6, 8, 10, 12**, // 14, 16, 20, **24**, // 28, 32, **36**, 40, 44, **48** and 52 (each week number, written in bold, indicates the weeks, at which the pairwise treatment comparisons will be made and // indicates the boundary for the study periods). In regard to interim analyses, only visits up to Week 12 will be included for IA1. IA2 will include data up to Week 24 for all subjects and beyond Week 24 for some subjects depending on the cut-off date (see Section 2). The analyses may be split by period or by combined periods depending on the tables produced for IA1 and IA2.

For all efficacy and quality of life analyses unless specified otherwise, baseline will be defined as the last non-missing assessment prior to the first dose of study medication (planned at Week 0).

For safety analyses, baseline will be defined differently according to the treatment period:

- Induction period: baseline will be defined as the last non-missing assessment prior to the first dose of study medication (planned at Week 0).
- Maintenance/Escalation period, Response Assessment/Dose Hold period and Overall study (all combined periods): baseline will be defined as the last non-missing assessment prior to the first dose of study medication (planned at Week 0) for all subjects randomized to M1095 or Secukinumab. For the subjects randomized to placebo, baseline will be the last non-missing assessment prior to the first dose of M1095 (planned at Week 12).

Unless otherwise stated, continuous data will be summarized by treatment group at each scheduled visit (including baseline) using the following summary statistics: number of non-missing observations (n), arithmetic mean, standard deviation, median, minimum and maximum. In general, summary plots over time will present means and standard errors. The number of decimal places for these statistics will be determined by the number of decimal places of the raw data or derived data where applicable: minimum and maximum will be presented with the same number of decimal places as for the raw data, mean and median with an additional decimal place and the standard deviation and/or standard error with two additional decimal places compared to the raw data.

Categorical data will be summarized in terms of the number of non-missing observations in the analysis population, frequency counts and percentages. Percentages will be displayed with one decimal place.

All statistical analyses will be performed using SAS v9.4 or higher.

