**Prior to Week 24:**

M1095 subjects in Arms 2 and 3 will receive placebo at Weeks 1, 3, 6, 10 and 14.

M1095 subjects in Arm 4 will receive placebo at Weeks 1, 3, 6, 10, 14 and 16.

M1095 subjects in Arm 5 will receive placebo at Weeks 1, 3 and 14.

Secukinumab subjects in Arm 6 will receive placebo at Weeks 6, 10 and 14.

Subjects randomized to 30mg or 60mg M1095 who do not achieve an IGA score of 0 or 1 at Week 12 will be dose escalated to 120mg q4w starting at Week 12.

Any subjects on M1095 who did not undergo dose escalation at Week 12 and who achieve an IGA score of 0 at Week 24 will have study drug withheld and will receive placebo q4w. Subsequently, if IGA score is 1 or more, these subjects will re-commence M1095 at the dose they received prior to

[figure not shown]
Week 24 on a q4w regimen at the visits scheduled by the protocol until the end of the treatment period. Dose will not be withheld for a second time, irrespective of subsequent IGA scores.

Subjects receiving secukinumab will continue to receive 300mg q4w throughout the study.

The subject blind will be maintained by the use of M1095 and matched placebo. The syringes used for all M1095 and placebo doses will be identical. All subjects will receive two injections of 1mL at each visit. There is also physical protection of the blind. Subjects will be asked to wear an eye-mask for all injections.

Randomization will be stratified by prior biologic use (yes or no) and weight ( $\leq 90\text{kg}$ ,  $>90\text{kg}$ ).

**Figure 1** Flow chart / design diagram

\* Prior to Week 24  
 M1095 subjects in Arms 2 and 3 will receive placebo at Week 1, 3, 6, 10 and 14.  
 M1095 subjects in Arm 4 will receive placebo at Week 1, 3, 6, 10, 14 and 16.  
 M1095 subjects in Arm 5 will receive placebo at Week 1, 3 and 14.  
 Secukinumab subjects in Arm 6 will receive placebo at Week 6, 10 and 14.

The last study drug injection is at Week 44, with key safety and efficacy evaluations at Week 48 and final safety and efficacy assessments at Week 52.

Planned number of subjects:	300
Diagnosis and main criteria for inclusion:	
Inclusion Criteria:
 
 
Ambulatory male and female subjects between 18 and 75 years of age at time of consent.
 

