4.9 Safety and Tolerability Data

Safety data will be summarized in the Safety Population by actual treatment group.

Unless indicated otherwise, safety variables will be summarized separately for the induction period (Week 0 to 12) and the overall study (Week 0 to Week 52) per actual treatment group (refer to Table 4.2 and Table 4.3 for details about defining actual treatment groups). Overall study corresponds to the time interval from Week 0 to Week 52 for the subjects who completed the study or from Week 0 to the last follow-up for subjects who discontinued. Please note that for the overall safety analyses, the baseline for subjects who were randomized to placebo will be the last non-missing assessment before the first dose of M1095.

No formal statistical treatment comparisons of the safety data are planned.

Further safety analyses may be conducted for the overall period, maintenance/escalation and response assessment/dose hold periods as described in

Table 4.13, Table 4.14 and Table 4.15 after assessment of safety data and if deemed necessary or if indicated otherwise in this section.

Table 4.13: Actual Treatment Groups and their Labels for Pooled Safety Analyses of the Overall Period

Actual Treatment Group*	Treatment Label
	Overall (Week 0-52) Per actual received doses
(1) - (Placebo at Week 0, 1, 2, 3, 4, 6, 8 and) M1095 120 mg at Week 12, 14, 16 and Q4W	Plac/120mg (x4), Q4 ^a
(6) - Secukinumab 300 mg at Week 0, 1, 2, 3, 4, 8 (and 12 and Q4W)	Secukinumab
(2a) - M1095 30 mg at Week 0, 2, 4, 8 and Q4W if no escalation at Week 12	30mg (x4), Q4 ^b
(2b) - M1095 120 mg Q4W from Week 12 if escalation at Week 12	Presented separately
(3a) - M1095 60 mg at Week 0, 2, 4, 8 and Q4W if no escalation at Week 12	60mg (x4), Q4 ^c
(3b) - M1095 120 mg Q4W from Week 12 if escalation at Week 12	Presented separately
(4) - M1095 120 mg at Week 0, 2, 4, 8 (and 12 and Q8W)	120mg (x4), Q8
(5) - M1095 120 mg Q2W at Week 0, 2, 4, 6, 8, 10 (and 12 and Q4W)	120mg (x6), Q4
	Total 120 mg ^d
	Total M1095 ^e

*: For (2a), (3a), (4), (5) and (6), subjects will be assigned to a treatment group based on the actual treatment they received most.

a: Plac/120mg (x4), Q4 include all subjects who were mostly administered M1095 120 mg from Week 12 to Week 44 having received placebo during the induction period. The data will only be presented from Week 12 for this treatment group.

b: 30mg (x4), Q4 include the data of:

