4.9.2.4 Clinical Laboratory Evaluations

All laboratory data up to Week 52 including serology tests (at screening only), pregnancy tests (women only) and urinalyses will be listed by treatment, subject, and visit/time. If reference normal ranges are available, laboratory abnormalities will be flagged and the CTCAE grade included.

Summary statistics of hematology, chemistry and urinalysis data and their change from baseline in SI units will be provided by treatment group and visit/time. Unscheduled measurements e.g. laboratory re-test due to abnormal laboratory results or unplanned visits due to safety concerns will be excluded from this analysis.

In addition, the number and percentage of subjects with abnormal, high or low, hematology, chemistry and urinalysis values will be summarized by treatment group.

Individual subject changes from baseline to worst post-baseline assessment in laboratory parameters graded using CTCAE will be summarized using shift tables by treatment group for the induction and overall period. The worst post-baseline laboratory assessment will correspond to the worst post-baseline CTCAE grade observed on-treatment over all visits (including scheduled and unscheduled measurements).

For non-graded laboratory parameters, shift tables will present the number and percentages of subjects within each baseline category (low, normal, high and missing) versus the post-baseline category (low, normal, high and missing). The categories will be defined by using the minimum and maximum values. Minimum/maximum baseline value will be the lowest/highest non-missing value observed during the baseline period i.e. before the first dose of study treatment. The minimum/maximum post-baseline laboratory assessment will be determined relative to the reference normal ranges i.e. to on-treatment lowest decrease and highest increase from minimum/maximum baseline over all visits (including scheduled and unscheduled measurements) for the considered period. In addition, a shift table from normal/high baseline category to low post-baseline category will be produced using the minimum value. Similarly, a shift table from low/normal baseline category to high post-baseline category will be produced using the maximum value.

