4.9.2.5 Adverse Events

Treatment-Emergent AEs (TEAEs) per treatment period are AEs that emerge while on study treatment during a given treatment period (e.g. induction period), having been absent pre-treatment, or that worsen during the considered period (e.g. induction period) relative to the pre-treatment state i.e. after baseline and on or prior to the date of the last visit of the considered period (e.g. Week 12 for the induction period). On study treatment during a treatment period is defined as the period from the first study treatment administration at the start of period (e.g. Week 0 for the induction period) up to the last visit of the treatment period for subjects who did not discontinue treatment during the considered period (e.g. Week 12 for the induction period) or for subjects who discontinued during the considered period, up to the end of the considered period or up to 8 weeks after the last dose of study treatment, whichever occurs first. TEAEs will be assigned to the actual treatment period to which they are considered treatment-emergent.

When considering the study overall, treatment-Emergent AEs (TEAEs) are AEs that emerge while on study treatment i.e. from the first study treatment administration up to 8 weeks after the last dose of study treatment, having been absent pre-treatment, or that worsen during study treatment relative to the pre-treatment state i.e. after baseline.

If the classification of an AE cannot be clearly established because of missing or incomplete date/time of AE, the AE will be classified as treatment-emergent. No imputation of missing or partial AE start and end dates will be performed.

To determine whether an AE is pre-treatment, on-treatment or post-treatment in case of partial or missing AE dates, the rules below will be followed:

- If the start date is incomplete and either the end date is incomplete or available:
 - if the non-missing part of the start date infers that the AE occurred post-treatment, the AE will be considered as post-treatment.
 - If the partial or complete end date indicates that the AE occurred prior to the first dose of study drug, the AE will be considered as pre-treatment.
 - If the partial start date does not give any evidence as to when the AE occurred during the study, and the end date infers that the AE stopped after the first dose of study drug, the AE will be flagged as on-treatment for all periods for which the first dose of study drug was started before the end of the AE.

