 - If the partial or complete start and end dates do not indicate as to when the AE started and ended compared to the first dose of study drug of any period, the AE will be flagged on-treatment for all periods.
- If both start and end dates are both missing: the AE will be considered on-treatment and therefore a TEAE for all periods.

To determine the worsening of an AE during study treatment, the maximum severity for each AE during the baseline period will be considered. In case of missing severity, the conservative approach below will be followed:

- If an AE has a missing severity during the study treatment, it will be defined as treatment-emergent.

- If the severity of an AE is missing at baseline and this event continues during the study treatment, this AE will be considered as treatment-emergent.

Adverse events of Special Interest (AESI) include cytopenias, liver function test changes/enzyme elevations, infections, injection-site reactions, allergic/hypersensitivity reactions, cerebrocardiovascular events, malignancies, depression, Crohn's disease and ulcerative colitis. Additional adverse events may be identified as being of special interest during the study and prior to first unblinding.

An overview table will present the number and percentage of subjects experiencing these types of AEs below by treatment:

- TEAEs,
- TEAEs by relationship to investigational product,
- serious TEAEs including deaths,
- TEAEs by maximum severity,
- deaths,
- and TEAEs leading to study treatment discontinuation.

This table will be produced for all separate treatment periods and the overall periods (refer to Table 4.3, Table 4.13, Table 4.14 and Table 4.15).

For the overall period, the exposure-adjusted incidence per 100 subject-years will also be presented. The exposure-adjusted incidence will be calculated by dividing the number of subjects with AEs by the total person years of exposure during the treatment period (refer to Section 4.7). This result will be multiplied by 100 to obtain the exposure-adjusted incidence per 100 subject-years.

The AESI will also be displayed with an overview table by treatment for each treatment period and the overall periods.

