The incidence of subjects with TEAEs will be summarized by the Medical Dictionary for Regulatory Activities (MedDRA) System Organ class (SOC) and Preferred Term (PT) and by treatment group. A subject with multiple AEs in the same SOC (or with the same PT) will only be counted once for that SOC (or PT). The PTs will be presented in decreasing order of frequency over all treatment groups within the SOC. Similarly, incidence tables will be produced for treatment-related TEAEs, for serious TEAEs, for TEAEs by maximum severity, for TEAEs leading to deaths and study drug discontinuations. In addition, the number and percentage of subjects with AESI will be presented by treatment group classed by SOC and PT. An additional summary table will be created to include the relatively common TEAEs i.e. with an incidence greater than 5%. All information obtained on adverse events will be listed by treatment group and subject. A listing of deaths will be also provided by indicating the study period in which the deaths occurred in the enrolled population.

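### Overall-period AESI, SOC/PT and worst-grade laboratory tables set a 40-week Plac/120mg column beside 52-week columns, with no stated adjustment for follow-up

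*SAP*

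**What the plan says.** SAP 4.1, Table 4.3, defines the columns for safety analyses of the overall period under a heading of Weeks 0 to 52. Footnote b restricts Plac/120mg (Arm 1): "The data will only be presented from Week 12 onwards for this treatment group". SAP 4.1 and 4.9 also reset this arm's baseline to the last value before its first M1095 dose, planned at Week 12. For the study as a whole, SAP 4.9 says "Overall study corresponds to the time interval from Week 0 to Week 52 for the subjects who completed the study".

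The outputs on these columns are described differently:

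- **TEAE overview (SAP 4.9.2.5):** counts and percentages, followed by "For the overall period, the exposure-adjusted incidence per 100 subject-years will also be presented".
- **AESI overview (SAP 4.9.2.5):** planned for each period and overall; no rate is mentioned.
- **SOC/PT tables (SAP 4.9.2.5):** incidence of subjects, each counted once. For AESI, "the number and percentage of subjects with AESI will be presented by treatment group classed by SOC and PT". AESI subgroup tables for the overall period follow the same form (SAP 4.12.2.3).
- **Laboratory shifts (SAP 4.9.2.4), induction and overall:** "The worst post-baseline laboratory assessment will correspond to the worst post-baseline CTCAE grade observed on-treatment over all visits".

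SAP 4.9 plans no formal comparison of safety data.

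**The concern.** The percentage of subjects ever affected depends on how long they are observed. A worst grade taken over all visits depends on how many samples are drawn. Both differ by design between Plac/120mg and the other columns of Table 4.3, and the heading over them gives the longer window.

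Safety and tolerability is a secondary objective. Because no testing is planned, these descriptive tables are the whole safety comparison. Arm 1 starts 120 mg on a different schedule from Arms 4 and 5, so readers will naturally compare those columns. A lower crude percentage in Arm 1 could then be read as better tolerability when part of it is shorter follow-up. Equal percentages could hide a higher event rate in Arm 1.

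No other planned table clearly fills the gap. Table 4.14 displays only the escalated 30 mg and 60 mg groups. Table 4.15 covers Weeks 24 to 52, split by dose hold, with no label for secukinumab. None gives Arms 1, 4, 5 and 6 a common window of Weeks 12 to 52, or of 40 weeks from first active dose.

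**Working it through.** The documents give no figure for this point and no safety event rates. Windows and draws below are counted from the documents; every incidence is an assumption.

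**1. Follow-up.** Arm 1: 52 − 12 = 40 weeks. Others: 52 − 0 = 52 weeks. Ratio 40/52 = 0.769. The exposure formula in SAP 4.7.1 agrees for a subject without dose hold. The protocol synopsis says "The last study drug injection is at Week 44", and 56 days are added: 44 − 12 + 8 = 40 and 44 − 0 + 8 = 52.

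**2. Scheduled chemistry/haematology draws (Protocol Section 8.1).** Weeks 1, 3, 6 and 10 have none.
- Others, post-baseline: Weeks 2, 4, 8, 12, 14, 16, 20, 24, 28, 32, 36, 40, 44, 48, 52 = 15.
- Arm 1, after its Week 12 baseline: Weeks 14 to 52 of that list = 11.

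**3. Crude incidence, equal constant hazard (assumption).** p40 = 1 − (1 − p52)^(40/52).

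| 52-week columns | Arm 1 | Gap (points) |
|---|---|---|
| 5% | 3.9% | 1.1 |
| 20% | 15.8% | 4.2 |
| 50% | 41.3% | 8.7 |
| 80% | 71.0% | 9.0 |

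With about 50 subjects per arm, the 20% row is 10.0 against 7.9 subjects. Equal crude percentages would correspond to a hazard 52/40 = 1.3 times higher in Arm 1.

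**4. Worst laboratory grade, equal independent chance per draw (assumption).** 1 − (1 − p)^(11/15): 20% becomes 15.1%.

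**5. Hazard falling after the first M1095 dose (assumption).** With exponential decay constant τ weeks and 20% at 52 weeks, p40 = 1 − exp(−H·r), where H = −ln 0.8 and r = (1 − e^(−40/τ))/(1 − e^(−52/τ)). For τ = 4, 8, 12 and 26 weeks, Arm 1 shows 20.0%, 19.9%, 19.6% and 18.3%.

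**6. Total M1095, five equal arms, constant hazard.** (4 × 20 + 15.8)/5 = 19.2%; (4 × 50 + 41.3)/5 = 48.3%.

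**7. Would the SAP's rate remove the gap?** SAP 4.9.2.5 divides subjects with events by total person-years, not censored at first event. Person-years per completer are 52 × 7/365.25 = 0.997 and 40 × 7/365.25 = 0.767. Constant hazard, per 100 subject-years:

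| 52-week incidence | SAP formula, others v Arm 1 | Censored at first event, both columns |
|---|---|---|
| 20% | 20.1 v 20.6 | 22.4 |
| 50% | 50.2 v 53.9 | 69.6 |

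The SAP formula nearly closes the gap for uncommon events and reverses it for common ones. Censoring at first event equalises the columns.

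The person-time also needs care. SAP 4.7.1 subtracts dose-hold time beyond 56 days, whereas the overall TEAE window runs "from the first study treatment administration up to 8 weeks after the last dose of study treatment". Protocol Section 6.0 counts placebo as study drug. If study treatment is read the same way, events during a hold are counted but part of the time is not.

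**8. Cutting at 40 weeks from first active dose.** Others: Weeks 2 to 40 of the list in step 2 = 12 draws. Arm 1: 11. Under the step 4 assumption, 20% becomes 1 − 0.8^(11/12) = 18.5%, so the remaining gap is 1.5 points.

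**The case against.** The strongest defence is that the columns are already aligned on first active dose. Arm 1 starts at its first M1095 dose with its baseline reset there, so early reactions are captured equally, and step 5 confirms almost no gap for them. Gaps of 4 to 9 points need a steady hazard and incidences of 20% or more, which the documents do not give; at 20% the gap is about two subjects. Footnote b discloses the Week 12 start. Induction safety is tabulated separately over the same 12 weeks for all arms. Table 4.15 offers a common Week 24 to 52 window for the M1095 arms shown. Laboratory summaries and boxplots by visit are not cumulative, and exposure in subject-years is reported by group. The AESI subgroup tables are optional.

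All of this stands, and it limits the size of the point. It does not align the overall AESI, SOC/PT and worst-grade tables for events that accrue over months.

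A reader might infer more than the documents support:

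- **That Arm 1 looks safer by construction.** Only a tendency is supported, and only for steadily accruing events.
- **That 11 against 19 visits measures the disparity.** Nineteen is the number of post-baseline visits with AE collection. AEs are collected continuously from consent, so time (77%) drives that gap. For laboratory tables the count is 11 against 15.
- **That every other column always holds 52 weeks.** This fits Table 4.3 for completers. In Table 4.13 the 30 mg and 60 mg columns take escalated subjects for Weeks 0 to 12 only, and Total 120 mg takes them from Week 12.
- **That exposure adjustment is ruled out for AESI and SOC/PT tables.** The text leaves this unclear.

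**Conclusion.** The point holds for the overall-period tables based on Table 4.3. Windows of 40 and 52 weeks, and 11 and 15 scheduled laboratory draws, are set side by side in summaries of subjects ever affected. No follow-up adjustment is stated beyond the TEAE overview. If the hazard since first M1095 dose is the same in each column, the expected crude percentage in Arm 1 cannot be higher than in the others.

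The size depends on event rates and timing that the documents do not give. Under a constant hazard the gap runs from 1.1 points (at 5%) to 9.0 points (at 80%); for events concentrated in the first weeks it is close to zero. The pull on Total M1095 is under 2 points at the 20% and 50% incidences shown, so a material distortion against secukinumab is not supported. The comparison is descriptive and no formal conclusion of the trial depends on it. This is a reporting weakness that is cheap to correct.

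**What to change.** - **SAP 4.9.2.5:** state that the overall-period AESI and SOC/PT tables show incidence per 100 subject-years beside the crude percentage. Censor each subject's time at the first event, and match time at risk to the window in which events are counted, including any dose hold. Extending the existing formula unchanged would over-correct common events.
- **SAP 4.9.2.4:** add a version of the worst-grade laboratory tables cut at 40 weeks from first active dose for every arm, with scheduled draws printed per column (12 against 11). A Week 12 to 52 restriction for all arms is not a good substitute: it would drop the other arms' first 12 weeks on drug and keep Arm 1's.
- **Table 4.3 and its outputs:** label the Plac/120mg column, and its contribution to Total M1095, as 40 weeks.

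The cost is SAP wording, longer tables and one repeated laboratory table. No data collection changes.
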